Cover Page

Official title of the study: A Randomized Clinical Trial to Assess the Efficacy of Intrauterine Balloon Compared to Intrauterine Contraceptive Device Plus Foley Catheter in the Therapy for Uterine Adhesion After Hysteroscopic Adhesiolysis. Date: 12/01/2017

Clinical Trial Registration Number: NCT02867202

Study protocol

The problem to be investigated

Project title: A Randomized Clinical Trial to Assess the Efficacy of Intrauterine Balloon Compared to Intrauterine Contraceptive Device Plus Foley Catheter in the Therapy for Uterine Adhesion After Hysteroscopic Adhesiolysis.

Research problem: This is a RCT designed to compare the efficacy of heart-shaped intrauterine balloon and Intrauterine Contraceptive Device Plus Foley Catheter in the prevention of adhesion reformation after hysteroscopic adhesiolysis. Background: The prevalence of IUAs varies from 0.2% in patients who undergo an intrauterine device insertion to 66.7% in patients with miscarriage curettage before. (Schenker & Margalioth, 1982) Hysteroscopic technique remain an accurate diagnosis for presence, degree of adhesions during the last two decades. (Fernandez, Al-Najjar, Chauveaud-Lambling, Frydman, & Gervaise, 2006)Hysteroscopic adhesiolysis currently become a safe and effective management to restore normal uterine cavity, however, the high incidence rate of postoperative adhesion reformation is a main challenge and difficult to solve, especially in patients with severe IUAs, in whom the recurrence rate was

reported up to 62.5%. (Yu, Wong, Cheong, Xia, & Li, 2008)Various adjunctive treatments have been proposed in an attempt to reduce postoperative recurrence. Despite the many proposed solutions, no particular method has proven to be the optima measure in preventing adhesion formation. Thereby, we put forward a new approach which combine intrauterine contraceptive device (IUD) with Foley catheter in the prevention of postoperative adhesion reformation, and there is as yet no study to confirm its value.

The aims: The aim of our study was to evaluate the efficacy of IUD plus Foley catheter and intrauterine balloon after hysteroscopic adhesiolysis in patients with moderate to severe adhesion according to the American Fertility Society (AFS) classification of intrauterine adhesions.

(v) The hypothesis: IUD plus Foley catheter presented a greater improvement in adhesion score than heart-shaped balloon in a retrospective study

2. Methods of investigation:

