Subjects: The patients were totally recruited from the 1st affiliated hospital of Wenzhou Medical University between August 2016 and December 2017.

Inclusion Criteria:

1) women aged 18 to 45 years.

2) patients had no history of hysteroscopic adhesiolysis.

3) agreed to have second-look hysteroscopy.

4) moderate to severe IUA (AFS score \geq 5) according to

American Fertility Society (AFS) scoring system.

5) written informed consent obtained.

Exclusion Criteria:

1) minimal adhesion (AFS score <5) and

2) previous hysteroscopic adhesiolysis.

3) Inability or refusal to provide informed consent

Design: Prospective, randomized, controlled trial.

Experimental procedure: The heart-shaped intrauterine balloon is designed to fit into the cavity of the uterus, and removed on the 7th day after surgery. And hysteroscopy was taken out again after two menstrual cycles to evaluate the uterine adhesions. Intrauterine Contraceptive Device Plus Foley Catheter are inserted into the uterine after a hysteroscopic adhesiolysis. Foley Catheter is removed after three days while IUD removed at the second hysteroscopy. Uterine adhesions were judged again at the second hysteroscopy. The presence of adhesion was confirmed and uterine anatomy had been assessed at first-look and second-look hysteroscopy.

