Cover Page

Official title of the study: A Randomized Clinical Trial to Assess the Efficacy of Intrauterine Balloon Compared to Intrauterine Contraceptive Device Plus Foley Catheter in the Therapy for Uterine Adhesion After Hysteroscopic Adhesiolysis.

Date: 12/01/2017

Statistical Analysis Plan

- 1. Measurements used: This study was taken out to compare two mechanical devices (intrauterine balloon and Intrauterine Contraceptive Device Plus Foley Catheter) in the therapy for intrauterine adhesions after hysteroscopic adhesiolysis. The efficacy in the prevention of adhesion reformation after hysteroscopic adhesiolysis for Asherman syndrome was compared between the groups.
- 2. Sample size calculation: Assuming that the adhesion recurrence rate was 46% in patients with intrauterine heart-shaped balloon insertion and in the group receiving intrauterine contraceptive device (IUD) plus Foley catheter was 18%, and accepting a type 1 error (α) of 0.05, and a type 2 error (β) of 0.10, the number of subjects required was 53 in each arm. After assuming the drop-out rate of 20%, the total number of subjects required was 132.
- 3. Statistical methods: Data analysis was performed with SPSS

version 22.0 (SPSS, Inc., Chicago, IL, USA), using two-sided test, and a p value < 0.05 was considered statistically significant. The continuous variables were analyzed by the Student's t test. The rate of reformation adhesions were described as percentages and were evaluated using chi-squared (χ 2) test or Fisher's exact test. The Mann-Whitney test was used to compare the reduction of AFS score between the groups.

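### The AFS score comparison uses no covariate, although first-look AFS is available for every eligible woman; adjusting for it may add precision at almost no cost.

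*SAP*

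**What the plan says.** SAP section 3 (Statistical methods) gives the score analysis in one sentence: "The Mann-Whitney test was used to compare the reduction of AFS score between the groups". It names no covariate, stratified test, regression model or effect estimate with an interval. I read the reduction as first-look minus second-look score.

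The Protocol supplies the baseline. Its exclusion criteria remove "minimal adhesion (AFS score <5"), and the inclusion criteria require a score of 5 or more. The experimental procedure adds: "The presence of adhesion was confirmed and uterine anatomy had been assessed at first-look and second-look hysteroscopy". A first-look score therefore exists for every eligible woman. The reduction also needs the second look, for which the SAP allows 20% drop-out.

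The Protocol's hypothesis is worded on the score scale: "IUD plus Foley catheter presented a greater improvement in adhesion score than heart-shaped balloon in a retrospective study". The sample size in SAP section 2 is not. It rests on recurrence of 46% versus 18%, from which "the number of subjects required was 53 in each arm". Recurrence has its own analysis: "The rate of reformation adhesions were described as percentages and were evaluated using chi-squared" or Fisher's exact test.

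**The concern.** The reduction open to a woman depends on where she starts. If women without recurrence finish near zero whatever their entry score, their reductions largely restate entry severity. Spread in entry scores then enters the comparison as noise, and a chance difference in entry AFS between arms can move the result.

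The stated hypothesis concerns improvement in the score, and this is the only planned analysis on that scale. It will therefore be read as a test of the hypothesis, although no power is claimed for it. As planned, it yields a p value and no estimate of how large the difference is.

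**Working it through.** **The plan's own figure.** With p1 = 0.46, p2 = 0.18, two-sided α = 0.05 and power 0.90, the unpooled formula gives

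n = (1.960 + 1.282)² × (0.46×0.54 + 0.18×0.82) / 0.28² = 53.07, stated as 53 per arm.

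For drop-out, 53/0.8 = 66.25, and 66 × 2 = 132. Both figures reproduce, and both concern recurrence, not AFS.

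**Where the gain comes from.** Let Y0 and Y1 be the first-look and second-look scores, ρ their correlation and k = SD(Y0)/SD(Y1). In units of Var(Y1):

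- variance of the reduction: 1 + k² − 2ρk
- residual variance after regression on Y0: 1 − ρ²
- difference: (k − ρ)², which is never negative and is zero only when ρ = k, that is, when the slope of Y1 on Y0 is 1.

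Ratio of regression variance to reduction variance, for assumed values:

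| k | ρ = 0.3 | ρ = 0.5 | ρ = 0.7 | ρ = 0.9 |
|---|---|---|---|---|
| 0.75 | 0.818 | 0.923 | 0.995 | 0.894 |
| 1 | 0.65 | 0.75 | 0.85 | 0.95 |
| 1.33 | 0.462 | 0.521 | 0.562 | 0.507 |

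At k = 1, if a mean-based comparison of reductions had 80% power with 53 per arm, the adjusted analysis would have 93.5%, 89.9%, 86.0% and 82.0% across the four columns.

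**Simulation on the trial's own recurrence rates.** The settings were 53 per arm, recurrence 46% versus 18%, and two-sided 0.05. There were 4,000 trials per power scenario, so the Monte Carlo standard error of each power is at most √(0.25/4000) = 0.8 points. The assumed grid has 3×3×3×3 = 81 scenarios:

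- entry AFS: uniform 5–12, skewed low over 5–12, or uniform 5–8
- log-odds slope of recurrence on entry AFS: 0, 0.2 or 0.4 per point
- second-look score without recurrence: 0, 0–2 or 0–4
- second-look score with recurrence: 1–8, 30%–90% of entry, or entry minus 0–2.

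Only the entry threshold of 5 comes from the documents; the upper limits are assumptions. The planned Mann-Whitney test (tie-corrected) was compared with linear regression of second-look AFS on arm and first-look AFS (HC3 errors).

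Power was 19%–88% as planned and 38%–89% adjusted. The gain was −3 to +32 points (median 11): at least 5 points in 61 scenarios, 1 point or less in 8, and slightly negative in 6. A repeat of the grid gave −3 to +34 (median 10).

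| Recurrent second-look score | Gain in power, points (median) |
|---|---|
| 1–8, unrelated to entry | +5 to +32 (19) |
| 30%–90% of entry | +4 to +20 (12) |
| Within 2 points of entry | −3 to +13 (3) |

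Single scenarios, planned versus adjusted:

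- Uniform 5–12, slope 0.2, non-recurrent 0, recurrent 1–8: 0.53 versus 0.77.
- The same with recurrent 30%–90% of entry: 0.72 versus 0.83.
- Worst case (low-skewed entry, slope 0.4, non-recurrent 0–4, recurrent close to entry): 0.79 versus 0.76.

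**Under no effect** (recurrence 32% in both arms, 10,000 trials per scenario), the planned test rejects in 4.4%–5.4% of trials and the regression in 4.1%–5.0%. Both hold their level.

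**Chance imbalance.** For whole-number entry scores uniform on 5–12, the SD is √(63/12) = 2.29. The standard error of the difference in means is 2.29 × √(2/53) = 0.445, so a difference of 0.75 or more arises in about 9% of randomisations. Over both 5–12 shapes the figure is 7%–9%. For 5–8 the SD is 1.12 and the figure is under 0.1%. Among null trials with such an imbalance (the 54 scenarios with entry 5–12), the planned test rejects in 4%–34% (median about 16%), and the adjusted analysis in 3%–6%.

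**The case against.** The strongest reply is that the simulated gain mixes three changes: reduction to second-look score, ranks to means, and no covariate to covariate. The reduction already uses the baseline by subtraction. In the same grid, a plain t-test on second-look AFS with no covariate comes within a median of 0.5 points of the regression (range −2 to +10). So much of the gain comes from no longer subtracting the entry score.

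That describes the mechanism but does not remove the gain. Regressing the reduction on arm and first-look AFS gives the same arm effect, with sign reversed, as regressing the second-look score. Adding the covariate to the planned outcome therefore is the change proposed. Against a t-test on the same reduction, the regression still gained a median of 7 points, and only about 2–3 points are due to ranks versus means. Regression also avoids having to guess in advance whether to subtract.

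Four points stand:

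- No magnitude can be derived from the documents, and scenario counts only describe an assumed grid.
- With entry scores confined to 5–8, the imbalance argument disappears.
- A rank test is a defensible choice for a bounded score with possibly many zeros.
- An interval could be had without a covariate, for example a Hodges-Lehmann interval on the reduction.

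**Conclusion.** The concern holds at the strength stated: adjusting for first-look AFS may add precision. It improves a valid analysis; the plan contains no error or bias on this point. Under the assumed distributions the effect on power runs from a loss of 3 points to a gain of 32. The gain is largest where second-look scores are unrelated to entry and close to nil where recurrent scores stay near entry. The protection against chance imbalance matters only if entry scores are widely spread. The comparison of recurrence and its sample size are untouched. Confidence is medium because the spread of AFS scores, their correlation and the definition of recurrence in AFS terms are all absent from the documents. The change is still worth making: the downside is small, and the hypothesis is worded on this scale.

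**What to change.** Replace the AFS sentence in SAP section 3 with wording such as:

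> Second-look AFS score will be compared between arms by linear regression on arm with first-look AFS score as covariate (robust standard errors), reporting the adjusted mean difference with 95% CI. A rank-based analysis (rank ANCOVA, or the Mann-Whitney test on the reduction) will be reported as supportive.

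The model and covariate should be fixed in advance, because choosing adjustment after seeing results invites selective reporting.

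The cost is one or two sentences and a standard regression on data already collected. The price is a linear-model assumption on a skewed score, which is why the rank analysis stays. In the simulations, rank ANCOVA had 1 to 12 points more power than the linear model when every woman without recurrence scored exactly 0, and 2 to 14 points less when those scores varied over 0–2 or 0–4.
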